The setting for this study is the CHOP primary care network. Women who intend to seek pediatric care for their new infants at CHOP primary care sites (Karabots, Cobbs Creek) will be enrolled from the Hospital of the University of Pennsylvania postpartum unit / newborn care units before hospital discharge or by phone within 4 weeks of a preterm birth. A maximum of 106 women will participate in this preliminary pilot trial. Enrollment will stop once feasibility is established.

Study Interventions and Measures:

[figure not shown]
Care Coordination after Preterm Birth is a behavioral intervention for women following preterm birth. Interventionists will provide health education, health care navigation, and motivational interviewing to ensure health care needs are met, positive health behaviors are adopted or sustained, and barriers to health are addressed.

The primary outcome of this study is acceptability and feasibility of the intervention. In addition, this preliminary trial will monitor postpartum visit attendance and other modifiable risk factors for recurrent adverse pregnancy outcomes.

Table 1: Schedule of Study Procedures

	Procedure	Screening & eligibility	Pre-intervention	Intervention	3 mon	6 mon
Measures to determine eligibility						
Screening eligibility	Health records review	X				
Measures of treatment feasibility and acceptability						
Recruitment rates	Study-team documented		X			
Reasons for non-participation	Study team documented (if available)		X			
Intervention fidelity	Study team documented			X		
Retention rate	Study team recorded				X	X
Treatment acceptability interview	Participant reported					X
Demographics, health utilization, and modifiable health behavior						
Participant demographics	Health record review and participant report			X		
Health care receipt	Health record review and participant report				X	X
Autonomy Support (Health Care Climate Questionnaire)	Participant reported		X			X
Autonomous Motivation (Treatment self-regulation questionnaire)	Participant reported		X			X
Contraceptive use	Health record review and participant report		X		X	X
Participant weight	Measured on scale or health record review or participant report		X			X
Tobacco use (30 days any versus none)	Participant reported		X		X	X
Mental health symptoms (Edinburgh Postnatal Depression Scale, Perceived Stress Scale)	Participant reported		X		X	X
Barriers to care	Participant reported		X		X	X
Sleep-related Impairment scale			X		X	X

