4.4 Study Population

4.4.1 Inclusion Criteria

- 1) Females age 14 – 45.
- 2) History of preterm birth at < 34 weeks gestation OR history of preterm birth at 34 – 36 weeks gestation with risk factors for recurrent preterm birth including: low preventive care utilization, tobacco use, obesity, depression or anxiety, history of unmet contraceptive needs.
- 3) Intention to seek infant pediatric primary care at one of the two study sites (Karabots and Cobbs Creek).
- 4) Medicaid insurance.

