5.4 Subject Completion/Withdrawal

Participants may withdraw from the study at any time without prejudice to their care. They may also be discontinued from the study at the discretion of the Investigator for lack of adherence to the study treatment or visit schedule, because of emergence of exclusion criteria, or to protect the subjects for reasons of safety or for administrative purposes.

Participants who do not receive all components of the intervention will still be included in the 3-month and 6-month assessments. Because the primary aim of this study is to determine feasibility and acceptability, efforts will be made to retain participants and to assess reasons for non-completion or withdrawal from the study.

If any adverse events occur that require clinical intervention during the course of participation, the PI or a co-investigator who is a licensed clinician will conduct a risk and safety assessment and make appropriate clinical referrals. If the investigators become aware of any serious, related, adverse events after study completion or withdrawal, the event will be recorded in a separate, coded REDCap database used to track attrition and adverse events.

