6.3.2 Sociodemographic factors

The following sociodemographic factors will be assessed at baseline only:

- Maternal age (years) (Health record review)
- Race (participant self-report)
- Ethnicity (Participant self-report)
- Educational attainment (Participant self-report)
- Estimated household income (Participant self-report)
- Prior pregnancies (Health record review)
- Complications of pregnancy including gestational diabetes or pregnancy-induced hypertension (Health record review)
- Chronic conditions including diabetes, asthma, hypertension, depression, or anxiety (Health record review)

The following demographic factors will be assessed at baseline and at 6-month follow-up and will both be collected via participant self-report:

- Household composition
- Relationship with other biological parent of child (if applicable) including married, cohabitating, not cohabitating but still in a relationship, no longer in a relationship but other parent actively involved in parenting

The following potential barriers to positive health behaviors will be assessed at baseline and at 3-month and 6-month follow-up and will all be collected via participant self-report:

- Health insurance will be assessed using item structure used in the Behavioral Risk Factors Surveillance Survey (at time of enrollment all participants should have Medicaid, however this may vary over time).⁶⁶
- Transportation needs will be assessed using items from the WellRx screening, which was developed in a Family Medicine setting and has been widely used.⁶⁷
- Child care will be assessed using items from the WellRx screening, which was developed in a Family Medicine setting and has been widely used.⁶⁷
- Food insecurity will be assessed with a two item screen that has been previously validated with families in pediatric settings. The two items are “within the past 12 months we worried whether our food would run out before we got money to buy more” and “within the past 12 month the food we bought just didn’t last and we didn’t have money to get more.”⁶⁸
- Employment status will be assessed using item structure used in the Behavioral Risk Factors Surveillance Survey and the Pregnancy Risk Assessment Monitoring System.^{66,69}

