9.4 Regulatory and Ethical Considerations

9.4.1 Data and Safety Monitoring Plan

In this minimal risk study, the primary anticipated safety risk relates to disclosure of sensitive information to study team members. This information includes information on mental health symptoms which are explicitly included in study data collection (Edinburgh Postnatal Depression Scale). In addition, though we are not explicitly asking participants to report on or discuss instances of abuse and neglect for either themselves or their infants, these issues may be disclosed. Finally, study team members may directly observe signs of abuse or neglect or signs of mental health deterioration.

We will ensure that all study team members have completed training for identifying abuse and neglect as well as severe mental health symptoms, and are also trained in reporting requirements. In addition, we have developed the following protocol to address any instances of safety concerns.

- **Mild to moderate behavioral health concerns that are not currently being treated:** Research staff will offer a resource sheet (included in IRB application as attachment) for community resources. This intervention will be embedded in two CHOP primary care sites. Therefore, study staff may also remind participants that social workers associated with their child's care site are available to help parents navigate access to behavioral health services for themselves.

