- **Severe behavioral health concerns that are not currently being treated:** This includes any mention of current thoughts or acts of self-harm or harm to others. In these situations, staff will notify the Principal Investigator (a licensed pediatrician) who will speak to the participant immediately, if time permits, or by phone as soon as possible. If indicated, suicidality will be assessed using the suicidal thoughts item from the Edinburgh Postnatal Depression Scale, which is currently the standard scale to assess maternal mental health in the Care Network. Item 10 of this scale reads "Over the last two weeks, the thought of harming myself has occurred to me..." response options include "yes, quite often," "sometimes," "hardly ever," and "never." Should there be an imminent risk to caregiver safety, study staff or the Principal Investigator will contact emergency services (911 or Pennsylvania mobile crisis services) for further suicide/homicide/risk assessment. If for some reason the Principal Investigator is not available in an emergency situation, study team members will contact the social work team associated with the child's care site for guidance.
- **Child abuse or neglect:** Should a caregiver spontaneously disclose incidents of abuse or neglect, we will file a report with Department of Human Services.
- **Intimate partner violence:** If a caregiver spontaneously discloses incidents of intimate partner violence, they will be offered a resource sheet (included in the IRB application as an attachment) about IPV resources. If they report ongoing intimate partner violence, they will be connected with the IPV specialist affiliated with the study sites to conduct further assessment and develop a safety plan. If there is concern for an immediate safety issue, study team members will immediately notify the principal investigator or, if she is not available for some reason, the IPV specialist associated with the child's care site.

Any referrals or follow-up activities related to the above safety concerns will ***not*** be documented in patient health records by the study team. In situations where an immediate safety concern was noted in study materials (recordings / transcripts), the transcript will be annotated to indicate any immediate or follow-up actions taken to address those concerns.

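### The severe-concern rule in 9.4.1 is limited by its heading to untreated concerns but by its text covers any mention of self-harm, so escalation is unclear for women already in treatment

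*Combined protocol and SAP*

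**What the plan says.** Section 9.4.1 names disclosure of sensitive information, including mental health symptoms, as the main anticipated safety risk. It introduces its list of responses with the statement that "we have developed the following protocol to address any instances of safety concerns". Two tiers deal with behavioral health:

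- **Mild to moderate.** The heading is limited to concerns not under current treatment. Staff offer a resource sheet and may mention the site's social workers.
- **Severe.** The heading is "Severe behavioral health concerns that are not currently being treated" and the first sentence is "This includes any mention of current thoughts or acts of self-harm or harm to others". Staff then notify the Principal Investigator, who speaks to the participant. The Edinburgh scale's self-harm item is used if indicated, emergency services are called if risk is imminent, and the site social work team is the back-up if the investigator cannot be reached in an emergency.

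The intimate partner violence tier in the same list has no treatment condition: "If there is concern for an immediate safety issue, study team members will immediately notify the principal investigator", with the site's specialist on such violence as the alternative contact.

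**The concern.** The heading and the first sentence give the severe tier different scopes, and they lead to different actions in one case: a woman in current mental health treatment who reports thoughts or acts of self-harm, or of harm to others. Staff who work from the heading could conclude that the tier is not meant for her. The mild-to-moderate tier does not name her either, because it carries the same qualifier.

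At stake is the speed with which a self-harm disclosure reaches a clinician. Being in treatment does not show that the treating clinician knows of the new disclosure. Section 9.4.1 also says that the study team will not record referrals or follow-up for these concerns in the health record, so the chart cannot be relied on to pass the information on.

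**Working it through.** The protocol states no figure on this point, so the main check is a comparison of texts.

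**1. Which text governs for a woman already in treatment?**

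| Text in 9.4.1 | Scope | Result for her |
|---|---|---|
| Severe-tier heading | Untreated concerns only | Tier does not apply |
| Severe-tier first sentence | Any current mention | Investigator is notified |
| Mild-to-moderate heading | Untreated concerns only | Tier does not apply |
| Lead-in to the list | Any instance of a safety concern | Some response is promised |

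The first sentence can be read as overriding the heading, or as giving examples within it. The protocol does not choose between these readings.

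**2. Does another section supply the missing instruction?**

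- Section 5.4 provides a risk and safety assessment by a licensed clinician whatever the treatment status. Its trigger is "If any adverse events occur that require clinical intervention during the course of participation". It does not say that a disclosure counts as such an event, and it names no immediate contact or back-up.
- The training described in 9.4.1 and 9.4.2 covers recognition, reporting requirements, immediate support and links to resources. It does not say whom to call about this participant.
- Sections 7.4.4, 8.1 and 8.2 cover the tracking, monitoring and reporting of adverse events. They are not a call chain at the time of disclosure.
- Under 9.4.1 the investigator reviews safety events at least every six months and urgently reviews unanticipated severe events. The urgent review serves reporting to the IRB and sponsor and revision of procedures. It presupposes that the event has already reached the investigator.

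**3. Is the case foreseeable?**

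- The risk factors that qualify a woman with a birth at 34–36 weeks (4.4.1) are "low preventive care utilization, tobacco use, obesity, depression or anxiety, history of unmet contraceptive needs".
- Section 6.1.1 lists treatment for depression or anxiety during pregnancy among the items taken from the record at screening. This is the closest evidence that treated women are expected.
- Section 6.3.2 records depression and anxiety as chronic conditions at baseline.
- None of the three exclusion criteria in 4.4.2 concerns mental health or its treatment.

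**4. How often might the rule be needed?**

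Inputs: maximum enrolment 106 (4.3.2); Edinburgh scale at baseline, 3 months and 6 months, so 3 administrations per woman (Table 1, 5.2, 5.3.1, 5.3.2).

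Scheduled administrations ≤ 106 × 3 = 318.

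The actual number may be lower. Enrolment can stop before 106 (4.3.2), and participants may not complete every procedure (4.1.2, 5.3). The bound counts all women, treated or not, whatever they answer. It covers scheduled questionnaires only; mentions during coordinator contacts are not in it.

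**The case against.** The strongest reply is that the instruction, and not its label, governs. The first sentence covers any mention, the emergency step states no treatment condition of its own, and the lead-in promises a response to any safety concern. To withhold escalation, staff would have to let a heading override all three. On this view the qualifier only separates known, managed conditions from new ones. Staff are also trained to identify severe symptoms, and that training, which is not in the documents, may already settle the matter.

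Much of this stands. Escalation is the safer reading and probably the intended one, and many staff would follow it. The other safeguards make a silent miss less likely. Having depression or anxiety is not the same as being in treatment, and the screening item concerns treatment during pregnancy, not at the time of disclosure. The comparison with the partner violence tier has limited force, because a treatment qualifier would not naturally arise there. The bound of 318 says nothing about how often the ambiguity would bite.

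What does not stand is the inference that no change is needed. The restrictive phrase is in the rule itself, the heading is what staff see first, and no other section corrects it.

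**Conclusion.** The concern holds as an ambiguity in a safety rule. For a woman already in treatment who mentions current self-harm or harm to others, 9.4.1 supports two different actions, and no other section gives staff an immediate contact for her. The conclusion rests on the wording alone and assumes only that some participants will be in treatment when they make such a disclosure, which the eligibility and screening sections make foreseeable. How many cannot be derived from the documents, and no count of missed escalations is claimed. No endpoint, estimate or analysis is affected. The point should be fixed because the consequence of the wrong reading is serious and the correction is small.

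**What to change.** In 9.4.1, delete the treatment qualifier from the severe-tier heading, or replace it with *regardless of treatment status*. Every report of current self-harm or harm to others would then trigger notification of the Principal Investigator, the back-up contact and, where risk is imminent, the emergency step. Align staff training, and any written aid that staff use, with the new wording. The qualifier can stay on the mild-to-moderate tier, where the action is a resource sheet.

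The cost is a one-phrase amendment, a short training update, and some extra notifications about women who are already in care.

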9.4.2 Risk Assessment

This is a minimal risk study. The safety plan described relates primarily to identification of safety risks not related to study procedures (i.e. the study should not increase the risk of mental health symptoms, but may identify these symptoms incidentally). Related to study procedures, it is possible that discussion with the study interventions or study data collection forms will cause psychological distress to participants. There is also some risk that increased monitoring from the health care team will increase utilization of health care services, which may carry some economic cost to participants. We do not anticipate any physical or societal harms. Our study design intends to minimize these harms by ensuring that study interventionists are trained to recognize distress, provide immediate support, and connect families to resources to that may assist with management of mental health symptoms, or with economic barriers to health care receipt.

9.4.3 Potential Benefits of Trial Participation

Benefits may benefit from increased access to preventive health care during the study period, and increased support for positive behaviors. These benefits may improve short-term health and wellbeing, medium range health outcomes such as improved outcomes in subsequent births, and long-term cardiovascular health. In addition, this trial may benefit participant offspring, if increased wellbeing allows greater attention to parenting activities, or if interventionists provide some care navigation relevant to infant health care.

9.4.4 Risk-Benefit Assessment

The risks associated with this study are minimal and generally no greater than the risks of receiving standard of care in the community (e.g. routine postpartum care).

9.5 Recruitment Strategy

Potentially eligible participants will be identified by screening health records in the newborn nursery and the neonatal intensive care unit at the Hospital of the University of Pennsylvania or by identifying women whose infants present for primary care at Karabots or Cobbs Creek. Chart review of women within four weeks of delivering a preterm infant (< 37 weeks) will assess for potential modifiable health risks, as well as other inclusion and exclusion factors. Next, potentially eligible women will be approached for recruitment and informed consent. Two eligibility factors may not be consistently documented in a health record (planned site of pediatric care for infant, any plans to move out of the area in the upcoming six months). These factors will be confirmed verbally before proceeding with other enrollment activities. Women will be approached by study staff via phone or in person during hospitalization following delivery, or when visiting their infant in the hospital. In the event that conditions related to COVID or other unanticipated events prevent the physical presence of study staff in the clinical setting we will develop a flier to be distributed at

discharge, allowing women to call a number to opt out of the study. This flier will be submitted to the IRB for review prior to use. We are requesting a waiver of consent and authorization for screening. Preliminary chart review estimates that approximately 100 eligible women deliver at HUP each year and choose to take their infants for pediatric care at one of the study primary care sites. We therefore expect it will be feasible to enroll 106 participants over two years.

9.6 Informed Consent/Accent and HIPAA Authorization

9.6.1 Waiver of HIPAA Authorization to Screen Medical Records

We are requesting a waiver of HIPAA authorization to screen health records for women following birth to identify potentially eligible participants. This will ensure that women who are contacted appear to be eligible based on chart review.

The use of health record data for eligibility screening involves no more than a minimal risk to the privacy of individuals. Identifiers for potentially eligible participants (name, room number, telephone number) will be stored in a secure REDCap database and will be destroyed within two weeks for any potentially eligible participant who has not been contacted or who has been contacted by declined enrollment. As noted above, screening summary data will be retained (number potentially eligible, number completed screening, number consented to study participation) but these data will not include any protected health information. Individual screening data will not be used for study purposes (beyond screening). Screening data will not be reused or disclosed for any reason.

The research could not practicably be conducted without the waivers. Due to the large number of women delivering at HUP and the frequency of rapid discharges, a requirement to obtain HIPAA authorization for screening could introduce bias into recruitment with women with longer length of stay more likely to be identified as potentially eligible. In addition, the research could not be conducted without access to this data as there would be no practicable way to identify potentially eligible women.

9.6.2 Combined Informed Consent-Authorization of HIPAA for Study Procedures

Members of the study team will be responsible for obtaining informed consent for study participation. For eligible participants, informed consent using a combined consent-HIPAA authorization will occur either in person or electronically, via a secure REDCap portal, pending participant preference and availability. When consent takes place in person, it will take place in the postpartum unit at HUP in a private room or in areas such as waiting areas that are semi-private and far enough away from other patients to maintain confidentiality. If informed consent is obtained electronically, the participant will receive a link to a secure REDCap portal in which they will be asked to enter their name and the date to indicate their consent. The participants name will associate the consent document with the enrolled participant. The REDCap portal will contain the exact same information in the same format as the paper consent form. The study team will email a copy of the completed electronic consent to the participant, with instructions to save a copy of this form.

For all consent procedures, potential participants will be given unlimited time to decide on participant. Potential participants will be informed of the nature of the research, the study procedures, the potential benefits and possible risks. Families will be informed that they are

free to decline to participate or to withdraw from the study, and that this decision will not influence any future medical care.

Though this study may enroll individuals aged 14 – 18, all participants will be considered adults for the purpose of this research. According to 45 CFR 46.402 children are persons who have not attained the legal age for consent to treatments or procedures involved in the research, under the applicable law of the jurisdiction where the research will be conducted. In Pennsylvania, individuals 14 years of age and older are legally able to consent to treatment related to reproductive health care and to care for their children. Because this research relates to reproductive health, in Pennsylvania women 14 years of age and older will be able to consent for this study independently.

